Combined phacoemulsification and viscocanalostomy with Ologen implant versus combined phacoemulsification and viscocanalostomy

Document Date: 1/5/2013

Introduction

Surgical treatment of glaucoma is indicated in cases of failure of medical treatment. Trabeculectomy is considered the standard surgical treatment of glaucoma. Nonpenetrating glaucoma surgeries, e.g. viscocanalostomy and deep sclerectomy, are becoming good alternatives. Viscocanalostomy has fewer complications than trabeculectomy, e.g. bleb leak, hypotony and bleb-related infections. ^[1–4]

Since the prevalence of both cataract and glaucoma increases with age, phakic patients who are scheduled for glaucoma surgery may also require cataract extraction, or patients scheduled for cataract surgery may be scheduled for combined surgery. Improvement of phacoemulsification techniques and stable anterior chamber depth with non-penetrating glaucoma procedures may favor combined viscocanalostomy and cataract surgery in patients with glaucoma and a coexisting cataract.^[4]

A biodegradable porous collagen-glycosaminoglycan copolymer matrix implant (Ologen[®]) is a simple chemical analog of extracellular matrices and has been used as an adjuvant to increase the long-term success of trabeculectomy. The degradation time of this type of implant is around 180 days; this implant consists of porcine based, lyophilized, crosslinked type I atelocollagen (\geq 90%) and glycosaminoglycans (\leq 10%). During trabeculectomy surgery it is placed subconjunctivally and acts as a spacer to mechanically separate the subconjunctival and episcleral tissues to decrease subconjunctival fibrosis.^[1,3]

Rationale

Primary open angle glaucoma is the second leading cause of blindness worldwide which needs effective attention otherwise it will lead to progressive optic nerve damage and eventual blindness.

The current surgical treatment of choice for medically uncontrolled glaucoma in association with cataract is combined phaco-trabeculectomy. However, this procedure is associated with both early and late postoperative complications.

Combined Non-penetrating glaucoma surgeries with phacoemulsification have been developed offering both surgeon and patient a safer, more convenient option.

With the use of Collagen implant with phaco-viscocanalostomy, it is expected to improve the pressure lowering effect of this procedure and increasing the success rate.

Research Question

Does phacoemulsification and viscocanalostomy with ologen implant have a better outcome, in patients with both cataract and primary open angle glaucoma, regarding postoperative IOP control and low complications rate, compared to phacoemulsification and viscocanalostomy alone?

Hypothesis

Our hypothesis is that using Ologen implant as a spacer in the subscleral reservoir in phacoviscocanalostomy reduces fibrosis and increase the success rate of this operation.

Aim of the Work

The Aim of this study is to evaluate the use of Ologen implant as an adjuvant in phacoviscocanalostomy in patients with coexisting cataract and glaucoma.

Objectives

- To estimate the number of patients with postoperative IOP ≤ 21 mmHg after phacoviscocanalostomy with ologen implant compared to phaco-viscocanalostomy alone 2 years after surgery.
- 2. To measure complete and qualified success rates after phaco-viscocanalostomy with ologen implant compared to phaco-viscocanalostomy alone 2 years after surgery.
- To report and describe early and late postoperative complications after phacoviscocanalostomy with ologen implant compared to phaco-viscocanalostomy alone 2 years after surgery.

Subjects and Methods

Before initiating this study, the protocol, the informed consent form and any other written information to be given to patients was reviewed and approved by the Ethics Committee of the Alpha vision center.

The investigator will explain to each patient the nature of the study, its purpose, the procedures involved, the expected duration, the potential risks, benefits involved, and any discomfort may be caused.

Each patient will be informed that participation is voluntary, that he or she may withdraw from the study at any time and without giving reasons. The withdrawal will not affect the subsequent medical or conservative treatment or relationship with the treating surgeon.

Technical Design

Center: Alpha vision center

Design: A prospective randomized controlled clinical trial.

Subjects: Patients will be collected from the outpatient clinic of Alpha vision center. The patient will be randomly assigned using simple randomization method to receive either Phacoemulsification and viscocanalostomy or Phacoemulsification and viscocanalostomy with Ologen implant.

Study sample: Based on previous studies by Shaarawy and Mermoud ^[5], the mean IOP at the first postoperative day was 6.4 (SD=3)mmHg for the DS-treated eyes, and 3.7 (SD=2)mmHg for the DSCI-treated eyes, the minimum total sample size of 32 will be sufficient to detect a power of 80% and a significance level of 5%. To allow for 25% losses, the sample was further increased to 81. Sample size estimation was performed by G power statistical package.

Inclusion criterion:

The inclusion criteria are the presence of significant cataract interfering with vision (visual acuity ≤ 0.5) in the presence POAG. Patients are included if cataract is associated with uncontrolled glaucoma, (IOP > 21 mmHg despite maximally tolerated medical therapy) or if the IOP is ≤ 21 mmHg with use of at least two antiglaucoma drugs with medication intolerance, poor patient compliance, patients cannot attend medical supervision or have visual field deterioration.

Exclusion criteria:

Patients will be excluded if they have closed-angle glaucoma, other types of open angle glaucoma (OAG), e.g. pigmentary glaucoma, inflammatory glaucoma or neovascular glaucoma, previous ocular trauma or surgery, lens subluxation or other eye diseases affecting the vision, e.g. anterior uveitis. Patients were also excluded if there is a large perforation of the Descemet's membrane with iris prolapse during surgery (cases with microperforation, which is defined as small perforation with no associated iris prolapse, occurring

during surgery will not be excluded) or if they have other intraoperative complications that might affect the IOP, e.g. vitreous loss.

Operational Design:

Patient histories will be taken including age, gender, previous ocular surgery, trauma or any previous ocular inflammation, e.g. keratitis, iridocyclitis, etc. Slit-lamp examination will be done for examination of anterior chamber angle, determination of the type of glaucoma and the degree of cataract, measuring IOP (using Goldmann applanation tonometer), assessment of optic nerve head and retinal examination, if possible. Visual acuity (VA) was expressed in decimal fraction.

Surgical procedures:

All operations will be carried out by one surgeon using peribulbar anesthesia.

After phacoemulsification, a traction suture in the cornea is made using 8-0 polyglactin 910 (Vicryl[®], Ethicon Inc, Bridgewater, NJ, USA).

A fornix based conjunctival flap is fashioned and no cautery is applied. Hemostasis is only achieved by using a microsponge soaked with 1/100,000 adrenaline. A superficial scleral flap of 5 x 5 mm is made and dissection is done 2 mm into the clear cornea. A smaller deeper flap of 4 x 4 mm is made until deroofing of Schlemm's canal is achieved. Decompression of the eye is done through one of the paracentesis incisions, then blunt dissection with a microsponge is done to create a descematic window that extended over Descemet's membrane until 1 to 2 mm inside the clear cornea. Subsequently, the sides of the deep flap is freed from the adjacent sclera by Vannas scissors and the deep flap is cut by the same scissors.

The juxtacanalicular trabeculum is removed and then the two openings of Schlemm's canal are cannulated on both sides using a viscocanalostomy cannula (Eagle labs, Rancho Cucamonga, CA, USA) and high-viscosity sodium hyaluronate (Healon GV; Abbott Medical Optic Inc., Santa Ana, CA, USA) is injected into the canal on both sides.

In the Phacovisco group, the superficial flap is closely sutured using four interrupted 10-0 nylon sutures, and then Healon GV is injected into the subscleral lake.

In the OloPhacovisco group, a 4 x 4 mm piece of Ologen[®] (Model: 862051 "12mm(D) x 1mm (H)") (Aeon Astron Europe B.V., Leiden, The Netherlands) is fashioned to be nearly of the same size as the cut deep scleral flap to fit inside the subscleral reservoir (Fig 2). Then the superficial flap is sutured tightly over it using four interrupted 10-0 nylon sutures (Ethilon[®], Ethicon Inc, Bridgewater, NJ, USA). Some air is injected from the paracentesis inside the eye. Then conjunctiva is closed using 8-0 polyglactin 910 sutures (Vicryl[®], Ethicon Inc, Bridgewater, NJ, USA).

Postoperative management included topical administration of 0.5% moxifloxacin drops with a tapered schedule of 1% prednisolone acetate. Antiglaucoma medication is ceased after surgery in all cases.

Follow-up:

Postoperatively, follow-up examination will be done on days 1, 7, 14 and 30, then every 2 months for 2 years. The follow-up examination includes assessment of IOP, VA and slit-lamp examination. Postoperative complications will be recorded. Signs of inflammation, such as cell infiltration and flare, is recorded and graded from 0 to 4.

Nd:YAG laser goniopuncture is considered in all cases with elevated postoperative IOP above 21 mmHg after discontinuation of corticosteroid eye drops for at least 14 days. The Nd:YAG goniopuncture is performed using an Ellex Super Q YAG laser machine (Ellex Medical Lasers Ltd., Mawson Lakes, SA, Australia) and the gonioscopy mirror of Goldman three mirror universal laser lens (Ocular, Bellevue, Washington, USA) with a laser power setting of about 3 to 6 mJ and using about 2 to 15 shots aiming at the opening of the trabeculo-Descement window, the number of laser shots needed to open the Descemet's membrane was counted and recorded in each group. Antiglaucoma drugs will be prescribed if the IOP is elevated above 21 mmHg after considering Nd:YAG laser goniopuncture.

The main outcome measures are the IOP at the 2-year follow-up and the overall success, which included complete success when IOP is \leq 21 mmHg without any antiglaucoma drugs, and qualified success if IOP is \leq 21 mmHg with the use of a single antiglaucoma medication. Failure is considered if IOP \leq 21 mmHg cannot be reached even with the use of a single antiglaucoma medication and after performing Nd:YAG laser goniopuncture, at any follow-up visit. The secondary outcome measures were surgical complications, the use and results of Nd:YAG laser goniopuncture and visual acuity results. The last data for failed cases were used for further statistical analysis.

RESULTS

Collected data will be presented in Tables and analyzed by computer software using appropriate statistical methods.

DISCUSSION

Discussion will be done on results compared to relevant literatures and scientific researches to explain the reasons for getting such results.

Conclusion and Recommendations

Conclusion and Recommendations will be derived from the findings of the study.

Statistical analysis plan:

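### The protocol specifies no allocation concealment, no time of assignment and nothing to keep the single surgeon unaware of the arm, although both arms share every step until implant placement and flap closure

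*Combined protocol and SAP*

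**What the plan says.** Under Technical Design the study is described by "Design: A prospective randomized controlled clinical trial". On recruitment it says "Patients will be collected from the outpatient clinic of Alpha vision center", and on allocation "The patient will be randomly assigned using simple randomization method to receive either Phacoemulsification and viscocanalostomy", with the implant version as the alternative. Neither the protocol nor its statistical analysis plan says more about allocation, and no masking of surgeon, patient or assessor is described.

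Under Surgical procedures, "All operations will be carried out by one surgeon using peribulbar anesthesia". Phacoemulsification, both scleral flaps, the descematic window, excision of the deep flap and cannulation of Schlemm's canal are described once, for all eyes. The window is taken "until 1 to 2 mm inside the clear cornea". The last shared step is the viscoelastic, which "is injected into the canal on both sides". Only then does the text divide:

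- Control: "In the Phacovisco group, the superficial flap is closely sutured using four interrupted 10-0 nylon sutures", followed by viscoelastic in the subscleral lake.
- Implant: "In the OloPhacovisco group, a 4 x 4 mm piece of" the collagen matrix is placed in the reservoir, and the flap is sutured over it.

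Under Exclusion criteria, patients are also removed for a large Descemet perforation with iris prolapse during surgery, or for other intraoperative complications judged capable of affecting IOP, with vitreous loss as the example.

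**The concern.** Simple randomisation describes how a sequence is generated. It does not say whether the person enrolling or operating can see the next assignment. Here that person's judgement enters at several points before the arms need to differ, and the Rationale and Hypothesis state an expectation that the implant will lower pressure further and raise the success rate. If the arm were known early, the choice of patients, the way the shared dissection is done and the decision to exclude an eye during surgery could each lean one way without anyone intending it. Such a difference would then be read as an effect of the implant. The planned between-group tests (t, Mann-Whitney, chi-square) include no adjustment for baseline factors, and the protocol does not provide for recording the window extent achieved.

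**Working it through.** The plan gives no figure on this point, so the main check is to set its sections side by side.

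**Where discretion exists before the arms diverge**

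1. *Entry (Inclusion criterion).* There are two routes. One requires IOP above 21 mmHg on maximally tolerated therapy. The other admits IOP of 21 mmHg or less on at least two drugs, given intolerance, poor compliance, inability to attend supervision or field deterioration. The second route rests partly on judgement. The share of patients entering by it is not given.
2. *Dissection (Surgical procedures).* Most dimensions are fixed for both arms: superficial flap 5 x 5 mm, deep flap 4 x 4 mm, superficial dissection 2 mm into clear cornea. The window extent is a range, and its upper limit is twice its lower (2/1).
3. *Exclusion during surgery (Exclusion criteria).* The perforation criterion is fairly specific. The second criterion is open-ended. The example given, vitreous loss, can arise in the shared part of the operation.
4. *Need to know the arm.* Nothing in the shared steps depends on it. The implant is cut to match the deep flap already removed, so the dissection does not have to anticipate the implant.

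**Illustration A: a systematic IOP difference between arms**

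Inputs: 81 recruited and 25% losses (Study sample) give 81 × 0.75 = 60.75, about 30 per arm. The 2-year SD of 3 to 4 mmHg and the bias b are assumptions. There is no true implant effect.

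- SE = SD × √(2/30): 3 × 0.258 = 0.77; 4 × 0.258 = 1.03.
- False-positive rate = P(|Z + b/SE| > 1.96).

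| b (mmHg) | SD 3 | SD 4 |
|---|---|---|
| 0 | 0.05 | 0.05 |
| 0.5 | 0.10 | 0.08 |
| 1.0 | 0.25 | 0.16 |

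**Illustration B: exclusions that depend on the arm**

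Assume 40 eyes per arm (81/2, rounded down), a true success rate p of 60% to 80%, and e eyes removed from one arm, all of which would have failed (the worst case). The observed rate is 40p/(40 − e).

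- e = 2: 24/38 = 63.2%, 28/38 = 73.7%, 32/38 = 84.2%, a gain of 3.2 to 4.2 percentage points.
- e = 4: 24/36 = 66.7%, 28/36 = 77.8%, 32/36 = 88.9%, a gain of 6.7 to 8.9 points.

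Both illustrations show only how sensitive the comparison is. Neither estimates what would happen in this trial.

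**The case against.** The strongest reply is that silence is not a defect in conduct. A reader might infer that allocation takes place in the clinic, or that the surgeon knows the arm before operating. The documents support neither. The clinic is only where patients are recruited, and no place, time or allocator is named. Allocation may already be concealed in practice.

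Other parts of the reply also have force:

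- Simple randomisation, unlike small blocks, makes the next assignment unpredictable, so steering of entry needs a visible list or assignment. That stands, but nothing in the plan rules out a visible one.
- Most surgical dimensions are fixed, and nothing suggests that dissection does differ by arm. That also stands. The point is that the plan does not prevent it.
- A reader might conclude that, with one surgeon, any such difference is inseparable from the implant effect. That goes too far. Imbalance in measured baseline factors can be examined and adjusted for, and window extent could be recorded and compared. Unmeasured selection could not be corrected. Using one surgeon also removes variation between surgeons, and an unmasked group of surgeons would raise the same problem.
- The illustrations rest on assumed biases, SDs and success rates. This is correct, and they carry no weight in judging how serious the point is.

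What remains is that concealment, timing and surgeon awareness are unspecified in a design where withholding the arm through the shared steps would be easy.

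**Conclusion.** The point holds as an omission with a practical remedy. The plan does not state allocation concealment, the time of assignment, or any provision to keep the single surgeon unaware of the arm during the steps common to both operations. Judgement-based entry at IOP of 21 mmHg or less, the window extent and the open-ended exclusions during surgery could therefore differ by arm. The documents do not show that they will, and the size of any bias cannot be derived from them. It is more than a reporting gap, because the time at which the arm is disclosed can be set so that all three are settled before anyone in theatre knows the arm. The conclusion assumes that the plan's silence reflects what is specified for the trial. If concealment up to that point is already practised, a sentence saying so resolves it. The change is worth making, mainly because it is inexpensive.

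**What to change.** Amend Technical Design to state that the random list is prepared by someone other than the surgeon and held in sequentially numbered, sealed, opaque envelopes. Existing theatre staff open the next envelope only after both ends of Schlemm's canal have been injected and any exclusion for an event in the shared steps has been decided and recorded. Entry, the shared dissection and those exclusions are then settled without knowledge of the arm. Exclusions made before the envelope is opened also come before assignment, so they do not disturb the randomised comparison.

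The cost is a short amendment, the envelopes, an implant on hand for every case and a brief pause in theatre. Whether existing staff can absorb the task is for the centre to confirm. If late opening is not feasible, concealed assignment before surgery would still protect entry, but not the dissection or the exclusions.

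The fix does not mask flap closure, goniopuncture, drug prescription or IOP measurement. The amendment should say so, so that the trial is not described as masked beyond the shared steps.

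### Allowing for 25% losses on a total of 32 gives 43 patients, not 81, so the only enrolment target does not follow from the figures offered for it

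*Combined protocol and SAP*

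**What the plan says.** The sample size is justified in one paragraph, Study sample, under Subjects and Methods. It takes its inputs from a cited study of deep sclerectomy with and without a collagen implant: "the mean IOP at the first postoperative day was 6.4 (SD=3)mmHg for the DS-treated eyes" and "3.7 (SD=2)mmHg for the DSCI-treated eyes". From these it concludes that "the minimum total sample size of 32 will be sufficient to detect a power of 80"%, at a 5% significance level. The next sentence sets the enrolment target: "To allow for 25% losses, the sample was further increased to 81". The calculation is attributed to G power.

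Three other places bear on the check:

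- Technical Design, Subjects, gives the allocation method without a ratio: "The patient will be randomly assigned using simple randomization method".
- The Statistical analysis plan specifies a two-tailed t-test between groups.
- The Follow-up section names the endpoints: "The main outcome measures are the IOP at the 2-year follow-up and the overall success".

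No other enrolment number, per-arm size or reason for the increase appears in the document.

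**The concern.** The paragraph offers one base (32), one loss rate (25%) and one result (81), and the three do not agree. A 25% allowance should add roughly a third to the base; here the sample is about two and a half times as large.

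Since 81 is the only enrolment target in the plan, the reader cannot tell which figure is wrong. If it is the base, the design assumption is misreported. If it is the loss rate, the attrition expected over two years of follow-up is misreported. If both are right, 81 was chosen for a reason that the document does not give. In a surgical trial, enrolling nearly twice the number that the stated calculation supports needs a stated reason, even if a good one exists.

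**Working it through.** **Inputs.** From Study sample: means 6.4 and 3.7 mmHg, SDs 3 and 2, power 80%, significance level 5%, minimum total 32, losses 25%, target 81. From the Statistical analysis plan: two-sided between-group test. Assumed, because no ratio is stated: 1:1 allocation.

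**Step 1: reproduce the base of 32.**

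- Pooled SD = √((3² + 2²)/2) = √6.5 = 2.55
- Standardised difference d = (6.4 − 3.7)/2.55 = 1.059
- Two-sample t-test (noncentral t, noncentrality d × √(n/2)): the solution for 80% power is n = 15.02 per arm, so 16
- 15 per arm: power 79.9%; 16 per arm: power 82.6%

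The total is 2 × 16 = 32, as stated. The inputs support 32 as a total, not as a per-arm number.

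**Step 2: apply the 25% loss allowance.**

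| Convention | Calculation | Total |
|---|---|---|
| Divide by the retained fraction | 32/0.75 = 42.7 | 43 |
| Same, rounded up within equal arms | 2 × 22 (16/0.75 = 21.3) | 44 |
| Multiply by one plus the loss rate | 32 × 1.25 | 40 |
| Stated in the plan | – | 81 |

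Check: 43 × 0.75 = 32.25, which keeps the required 32. The gap to 81 is 37 to 41 patients, depending on the convention.

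**Step 3: work back from 81.**

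- Loss rate implied by 32 and 81: 1 − 32/81 = 60.5%
- Base implied by 81 and 25%: 81 × 0.75 = 60.75, about 61; by the other convention, 81/1.25 = 64.8, about 65

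Neither 61 nor 65 appears in the document.

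**Step 4: try other routes to 81.**

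- Higher power, same inputs, divided by 0.75: 90% gives 40 → 54; 95% gives 50 → 67; 99% gives 68 → 91
- Allowance applied twice: 32/0.75/0.75 = 56.9, so 57
- 32 read as per arm: 64 × 1.25 = 80, or 64/0.75 = 85.3, so 86

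None gives 81.

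**Step 5: what 81 would deliver.** After 25% losses, 60.75 remain, taken as 60.

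- At 30/30, power for d = 1.059 is 98.1%, and the standardised difference detectable with 80% power is 0.736.
- Simple randomisation need not give equal arms. With equal assignment probability (assumed), the central 95% binomial range for 60 patients runs from 22/38 to 38/22. At 22/38, with a common SD of 2.55, power is 97.3% and the detectable difference is 0.763.

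**The case against.** The strongest reply is that nothing is lost. The plan calls 32 a minimum, 81 exceeds it, and power on the plan's own assumption is about 98% after the stated losses. No error rate, estimate or analysis changes. That is correct, and it limits the point to one of documentation and traceability. It does not make the sentence true, because the sentence gives the loss allowance as the reason for 81.

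A second reply is that 32 was carried forward as a per-arm number. Doubling to 64 and multiplying by 1.25 gives 80, one short of the target. This may well be how the slip arose. It does not support the figure: the text says total, the stated inputs reproduce 32 only as a total, and 80 is not 81.

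A third reply is that correcting the sentence to 43 prejudges which number is wrong. There is force in this. The figure of 43 is only what follows if 32 and 25% are both right. The authors may find that the base, the loss rate or the target was misreported, and the fix must leave room for that.

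Finally, the unequal-arm figures in Step 5 use a common SD although the plan's SDs are 3 and 2. With those SDs, power at 22/38 can move by up to about two percentage points, depending on which arm is smaller and which form of the t-test is used. The figures serve only to show that there is no shortfall, and that conclusion is unaffected.

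**Conclusion.** The concern holds. With the stated base and loss rate the target is 43 (40 to 44 by convention), against 81 in the plan; reaching 81 would need 60.5% losses or a base of about 61 (65 by the multiplying convention). The inflation arithmetic needs no assumption beyond the plan's own 32 and 25%. The reproduction of 32 assumes 1:1 allocation and uses the two-sided test named in the analysis plan.

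The correction should be made, but the error does not threaten power for the day-1 effect. Reproducing 32 also does not endorse day-1 IOP as the basis for a trial whose main outcomes are 2-year IOP and overall success; that is a separate question. The detectable difference of about 0.74 applies to a continuous outcome and says nothing about the binary success outcome. It cannot be turned into mmHg, because no SD for 2-year IOP is given.

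**What to change.** In Study sample, reconcile 32, 25% and 81:

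1. If the base and loss rate stand, say that allowing for 25% losses takes the minimum total of 32 to 43 (44 with equal arms).
2. State the actual reason for enrolling 81, or the base and loss rate actually used to reach it. Do not choose values now because they happen to yield 81.
3. If no record of that step survives, say that 81 was not derived from the calculation.

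Optional addition: *After 25% losses about 60 patients remain; if the arms are equal (30 each), this gives 80% power for a standardised difference of about 0.74 on a continuous outcome such as 2-year IOP; this does not cover the binary success outcome.*

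The cost is one corrected sentence and one optional sentence, with no change to enrolment or analysis.

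### Patients enter on either side of the 21 mmHg success threshold, yet neither randomisation nor the success test uses entry route; separately, Objective 1 lacks the drug limit that defines success

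*Combined protocol and SAP*

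**What the plan says.** The Inclusion criterion gives two ways in. The first is "IOP > 21 mmHg despite maximally tolerated medical therapy". The second is an IOP at or below 21 mmHg "with use of at least two antiglaucoma drugs with medication intolerance, poor patient compliance", inability to attend supervision, or field deterioration.

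Under Technical Design, patients are "randomly assigned using simple randomization method"; no stratification factor is named. The Statistical analysis plan compares categorical variables by chi-square, with no stratum or covariate.

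The outcome definitions (end of Follow-up) set complete success at 21 mmHg or below on no drug, and qualified success at the same level "with the use of a single antiglaucoma medication". An eye fails if it cannot reach that level on one drug after goniopuncture.

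The first item under Objectives is "To estimate the number of patients with postoperative IOP ≤ 21 mmHg after phacoviscocanalostomy with ologen implant compared to phaco-viscocanalostomy alone 2 years after surgery". It mentions neither drugs nor baseline. All glaucoma drugs stop at surgery (Surgical procedures). They may be restarted if IOP exceeds 21 mmHg once goniopuncture has been considered, with no stated maximum number (Follow-up). The last data of failed cases are used in the analysis, but the plan does not say whether these are the values at failure or at 2 years.

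**The concern.** The two routes separate patients at the pressure that later decides success. An eye above 21 mmHg on all the drugs it tolerates has further to go than one already below that level on drugs, so success probably differs by route. If it does, a chance excess of second-route eyes in one arm flatters that arm. Simple randomisation does nothing to prevent this, and the planned test does nothing to correct it, although the route must be known for every patient to establish eligibility.

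Objective 1 has a smaller, separate problem. An eye at 18 mmHg on two drugs before surgery and again at 2 years could be counted as controlled. The outcome definitions do not count it as a success, and they class it as a failure if one drug was not enough. Two analysts could report different Objective 1 counts from the same data.

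**Working it through.** **Inputs from the documents.** N = 81 (Study sample); simple randomisation (Technical Design); chi-square, two-sided 5% (Statistical analysis plan). The allocation ratio is not stated; 1:1 is assumed.

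**Inputs the documents do not give, taken as ranges.** Second-route share q = 20, 30 or 50%. Control-arm success in second v first route of 0.8 v 0.6 (weak), 0.9 v 0.5 (strong) or 0.95 v 0.4 (very strong). Implant effect: a common odds ratio of 4, which for example moves 0.5 to 0.80 and 0.9 to 0.97.

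**The plan's own figure.** The only power calculation concerns mean IOP on day 1: difference 6.4 − 3.7 = 2.7, SD = √((3² + 2²)/2) = 2.55, standardised difference 1.06. A two-sided t-test with 80% power needs 15.02, so 16 per arm and 32 in total, as stated. It says nothing about success or entry route and is not used further.

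**Step 1: imbalance in entry mix.** The SD of the arm difference is about 2√(q(1−q)/81). At q = 0.5 this is 2 × 0.5/9 = 0.111. Simulation (50,000 trials each) gave:

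| Second-route share | SD | P(difference > 10 points) | P(difference > 20 points) |
|---|---|---|---|
| 20% | 0.089 | 26% | 2% |
| 30% | 0.102 | 33% | 5% |
| 50% | 0.112 | 37% | 8% |

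**Step 2: what imbalance does to the success comparison.** If success differs by 30 to 40 points between routes (assumed), a 20-point imbalance moves the arm difference by 0.20 × 0.30 = 6 to 0.20 × 0.40 = 8 points. For scale, take q = 0.5 and success 0.9 v 0.5 with no implant effect. The outcome variance is 0.7 × 0.3 = 0.21, of which 0.5² × 0.4² = 0.04 (19%) lies between routes. The SE of the arm difference is √(0.21 × 4/81) = 10.2 points; the between-route part alone is √(0.04 × 4/81) = 4.4 points. Route is a real but minor part of the noise.

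**Step 3: type I error and power.** Chi-square without continuity correction against Mantel-Haenszel stratified by route, 20,000 trials per setting, N = 81:

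| Success by route | q | Chi-square power | Stratified power | Gain (points) |
|---|---|---|---|---|
| 0.8 v 0.6 | 20 / 30 / 50% | 71.4 / 68.0 / 62.8% | 70.9 / 68.2 / 63.0% | −0.5 / 0.2 / 0.2 |
| 0.9 v 0.5 | 20 / 30 / 50% | 72.6 / 67.3 / 55.7% | 75.0 / 70.7 / 60.3% | 2.4 / 3.4 / 4.6 |
| 0.95 v 0.4 | 20 / 30 / 50% | 72.5 / 65.9 / 49.9% | 77.5 / 72.6 / 60.0% | 5.0 / 6.7 / 10.1 |

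With no implant effect, rejection rates were 4.7 to 5.3% for chi-square and 4.7 to 5.2% for the stratified test. With 61 patients left after 25% losses (81 × 0.75 = 60.75), the gains run from −0.7 to 8.0 points.

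**Step 4: upper bound on dilution of Objective 1.** Suppose every second-route eye counts as controlled in both arms and first-route control is 0.60 v 0.85 (assumed). The rate in each arm is q + (1−q)p, so the difference is (1−q) × 0.25: 20, 17.5 and 12.5 points at q = 20, 30 and 50%. Power at 40.5 per arm falls from 72% (q = 0) to 59, 52 and 37%. The number per arm for 80% power rises from 49 to 67, 79 and 118. This is a worst case, because it assumes that all second-route eyes are controlled whatever their treatment.

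**The case against.** The case against is strong on several counts. An unadjusted chi-square in a randomised trial is valid, and its error rate already allows for chance imbalance. The documents give no evidence that entry route is prognostic. The second route includes poor compliance and field deterioration, and untreated pressures may overlap widely between routes. A 50:50 mix gives the largest imbalance, and with a weak route effect the gain is nil. A small second-route stratum is also sparse: 30% of 81 is about 24 eyes, and at 90% success only about two would fail. All of this stands. It limits the size of the point, but does not remove the case for using a baseline variable that must already be known. Sparseness mainly affects the by-route description, since the stratified test kept its 5% level even at a 20% share with 95% success.

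On Objective 1, a reader might infer that it can be met without any benefit from surgery and so could produce a spurious implant effect. The documents do not support that. Both arms have surgery, and randomisation places second-route eyes in both, so they can dilute the contrast but not create one. Drugs are stopped at surgery, and Objective 2 already applies the drug limit. If failed eyes carry their value at failure, the two-drug eye would have been above 21 mmHg and would not count. The plan does not settle that reading, so the ambiguity remains.

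**Conclusion.** The point holds as a modest loss of precision and an uncorrected chance imbalance. It is not an invalid test. On the assumed ranges, ignoring entry route costs about 0 to 5 points of power in most scenarios and up to about 10 if the route effect is very strong, with type I error near 5% either way. An imbalance above 20 points, enough to move the success difference by 6 to 8 points, arises in 2 to 8% of trials. These figures rest on assumed route shares, success rates, a common odds ratio of 4 and 1:1 allocation. It would go too far to call the route strongly prognostic as a fact.

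The Objective 1 wording is a secondary defect confined to that objective. The complete and qualified success definitions are unaffected: a second-route eye must do at least as well on fewer drugs to count.

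**What to change.** - Make the between-arm comparison of success a Mantel-Haenszel test stratified by entry route. An analysis adjusted for baseline IOP and drug count would serve equally. State the choice before the data are seen.
- Report success by arm within each route, and baseline IOP and drug count by arm.
- Align Objective 1 with the outcome definitions by stating the drug count: the number at or below 21 mmHg on no drug, and on at most one drug. Accept that it then overlaps with Objective 2, or merge the two.
- State whether a failed eye enters the 2-year analysis with its value at failure or at 2 years.

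The cost is wording. Baseline IOP is measured, and the drug count is needed to apply the second entry route, so no patients, visits or measurements are added. The small downside is a sparse second-route stratum with few failures, so the by-route results should be descriptive.
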